8.4 Medical History

The medical history data collected in the main study will be summarized for the patients in the OLE by System Organ Class (SOC) and preferred terms based on the coded data by the Medical Dictionary for Drug Regulatory Activities (MedDRA). The count and percentage of ongoing medical condition per preferred terms will also be provided.

9 ANALYSIS OF SAFETY ENDPOINTS

9.1 Adverse Events

AEs will be coded using MedDRA v20.1. TEAEs for each 12 month period will be defined as those that start in each 12 month period and separately for Period V on PEN, which will be cumulative. The denominator used for calculation of AE rates will be the number of patients at the beginning of each period or year. For patients who have gaps in treatment, the events that start in the gap will be included in the prior treatment period. In addition, a summary of AEs for the entire extension period will be provided.

The results will be presented:

- by order of the frequency of AEs by the MedDRA preferred term (PT)
- by severity of AEs
- by the relationship of AEs to the study drug
- and all SAEs

Patient incidence of AEs of special interest will also be summarized overall and by SOC through the entire extension period. The AEs of special interest are:

Adverse Event of Special Interest	MedDRA v20.1 Definition Criteria
Glucose metabolism impairment	Hyperglycaemia/new onset diabetes mellitus (standardized medDRA queries [SMQ]) Full Scope
Thyroid function impairment	Thyroid dysfunction (SMQ) Full Scope
Intracranial hypertension	Increased intracranial pressure disorders (high level term [HLT] - All Paths)
Neoplasias	Malignancy (SMQ) Full Scope
Intracranial aneurysm	Central nervous system aneurysms and dissections (HLT - All Paths)
Immunogenicity (including positive anti-drug antibody and allergic reactions) and Hypersensitivity	Laboratory result parameter: Anti somatrogon antibody or Neutralizing Antibody present, Anaphylactic reaction (SMQ) Narrow Scope, Angioedema (SMQ) Narrow Scope, Hypersensitivity (SMQ) Narrow Scope
Injection site reactions (including lipoatrophy/skin dystrophy)	Injection site reactions (HLT - All Paths) and select PTs (Lack of injection site rotation, Lipoatrophy, Skin hypertrophy, and Skin dystrophy) and PTs containing 'Administration site'
Epiphysiolysis	PT Epiphysiolysis
Haemangioma of skin	PT Haemangioma of skin
Oedema	Oedema NEC (HLT - All paths) and Total fluid volume increased (HLT - All Paths)
Scoliosis	PT Scoliosis
Acute and chronic pancreatitis	Acute and chronic pancreatitis (HLT - All Paths)
Increased Protein kinase	PT Blood creatine phosphokinase increased

Adverse Event of Special Interest	MedDRA v20.1 Definition Criteria
Adrenal cortical hypofunctions	Adrenal cortical hypofunctions (HLT - All Paths)
Myalgia	PT of Myalgia
Myositis	PT of Myositis
Arthralgia	PT of Arthralgia

A listing of TEAEs that lead to withdrawal from the study will also be provided.

Missing values will be treated as missing except for causality, intensity, and outcome of an AE, at which occurrence a "worst case" approach will be taken in the analysis. Thus, if causality is missing the AE will be regarded as related to the investigational medicinal product (IMP), if the intensity is missing the intensity of the AE will be regarded as severe, and if the outcome is missing and the stop date is not provided the outcome is regarded as "ongoing." If the classification of SAE (seriousness) is missing, all efforts should be made prior to database lock to make sure that this information is available.

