7.1 ADVERSE EVENTS

Information about all adverse events, whether volunteered by the patient, recorded in the patient's diary, discovered by investigator questioning, or detected through physical examination, laboratory test or other means, will be collected and recorded on the Adverse Event Case Report Form and followed-up as appropriate. An adverse event is defined as any undesirable sign, symptom or medical condition occurring after starting the study drug (or therapy) even if the event is not considered to be related to the study drug (or therapy). Study drug (or therapy) includes the drug (or therapy) under evaluation.

Medical conditions/diseases present before starting the study treatment are only considered adverse events if they worsen after starting study treatment (any procedures specified in the protocol). The period for collecting adverse events begins after signing the informed consent form and continues until 4 weeks after the patient has received the last dose of study treatment.

OPKO Biologics	Protocol for Clinical Study CP-4-004	Page 85 of 133
Effective Date: Date of final electronic approval		

Abnormal laboratory values or test results constitute adverse events only if they induce clinical signs or symptoms, are considered clinically significant or require therapy. Such adverse events are recorded on the Adverse Events Case Report Form under the signs, symptoms or diagnosis associated with them.

Any AE that occurs in the course of a clinical study must be monitored and followed-up until:

- It has receded
- Pathological laboratory findings have returned to normal
- Steady state has been achieved

It is the responsibility of the Investigator to ensure that any necessary additional therapeutic measures and follow-up procedures are performed.

Whenever possible, the Investigator(s) should always group signs and symptoms into a single term that constitutes a single unifying diagnosis. The Investigator's opinion of the association of each AE to study drug, the duration, frequency, intensity, countermeasures and the outcome of each AE will be documented.

The event's **relationship to the study drug** should be indicated according to the following **definitions**:

Relationship to study drug definitions:

1. Not related	
• This category applies to those adverse events which, after careful consideration, are clearly and incontrovertibly due to extraneous causes (disease, environment, etc.)

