8.5 SAFETY EVALUATION

The assessment of safety will be based mainly on the frequency of AEs, frequency of anti-MOD-4023 antibody development and on the number of laboratory values that fall outside of laboratory normal ranges. Other safety data (e.g. vital signs, special tests, etc.) will be considered as appropriate.

AEs will be listed by treatment group and patient for the treatment phase. AEs will be summarized by presenting, for each treatment group, the number and percentage of patients having any AE, having an AE in each body system and having each individual AE. Any other

OPKO Biologics	Protocol for Clinical Study CP-4-004	Page 97 of 133
Effective Date: Date of final electronic approval		

information collected (e.g. severity or relatedness to study medication) will be listed as appropriate.

Summaries and analyses will be based on treatment-emergent adverse events (TEAE), which are defined as AEs occurring after the first administration of study medication (as recorded on the study discontinuation / end of study CRF) or AEs present before the first dose and ongoing after administration with increased severity. Other AEs (pre-treatment AEs) will only be listed.

If appropriate, laboratory and/or ECG data will be summarized by presenting shift tables using extended normal ranges (baseline to most extreme post-baseline value), by presenting summary statistics of raw data (means, medians, standard deviations, ranges) and change from baseline values and by the flagging of notable values in data listings.

Blood glucose, HbA1c, cortisol, thyroid panel tests and lipid panel tests (with special attention on LpA) will be evaluated using standard descriptive statistics, the number of patients who had values outside normal values, and by listing values considered clinically relevant by the investigator.

Data from other tests (e.g. blood pressure or vital signs) will be listed, notable values will be flagged, and any other information collected will be listed as appropriate. Summary statistics will be given where appropriate.

In addition the number and percentage of patients developing antibodies, including neutralizing antibodies, will be summarized by cohort.

Local tolerability will be summarized based on the investigator's assessments of pain, tenderness, erythema, warmth and swelling which will be done by a scale and predetermined schedule during intensive PK/PD sampling.

The safety analysis will be performed based upon the safety analysis subset.

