2 INTRODUCTION

This statistical analysis plan (SAP) details data analysis of the OLE periods of protocol CP-4-004, version 10, 3 Oct 2017 (_______). The first 12 months of this study consisted of two periods, Periods I and II, with the primary objective of evaluating three doses of somatrogon to a commercially available standard daily recombinant human growth hormone (rhGH) formulation. The ongoing long-term open-label treatment covered by this plan starts with Period III (after the completion of Period II), through Period V (treatment with PEN formulation) to the end of study for all patients. This plan provides more specific details for the analysis than in the protocol, and any differences from the analysis as outlined in the protocol will be documented in this plan. Any difference from this plan that arise during the actual analysis of the data will be documented in the study report.

The International Nomenclature Name for MOD-4023 is somatrogon, which will be used subsequently throughout this document. The somatrogon designation was assigned after the commencement of CP-4-004.

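### SAP 9.1 assigns treatment-emergent adverse events to OLE years and to PEN by start date alone, with no rule for ongoing events that worsen and no note of the difference from protocol 8.5

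*SAP*

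**What the plan says.** SAP 9.1 gives the only TEAE rule in the SAP: "TEAEs for each 12 month period will be defined as those that start in each 12 month period". Period V on PEN is counted separately by the same rule, the PEN count being cumulative. Events that begin in a treatment gap go to the period before the gap. Rates use the number of patients at the start of the period or year. One overall display is added: "In addition, a summary of AEs for the entire extension period will be provided". No inclusion rule is given for it. Results are also shown "by severity of AEs", without saying whether the initial or the maximum grade is meant.

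Protocol 8.5 has a definition in two limbs. The first is "which are defined as AEs occurring after the first administration of study medication". The second is "AEs present before the first dose and ongoing after administration with increased severity". Protocol 7.1 takes a similar line on conditions that existed before treatment, which "are only considered adverse events if they worsen after starting study treatment".

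SAP 2 undertakes that "any differences from the analysis as outlined in the protocol will be documented in this plan". No section of the SAP keeps a worsening limb, and none mentions that it has gone.

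**The concern.** Safety is the primary objective of this SAP, expressly including the transition to PEN (SAP 3.1.1). The patients are not newly treated: all have had a year of growth hormone before Period III. Several adverse events of special interest in SAP 9.1, such as scoliosis, thyroid dysfunction, impaired glucose metabolism and adrenal hypofunction, can persist for long periods. For such events, progression may be the signal, and a count by start date cannot show it in the period where it happens.

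The former Genotropin patients are the clearest case. Their first somatrogon dose is at the start of Period III (SAP 4.2), and SAP 9.13 starts their somatrogon exposure there. If an event began on Genotropin and became worse on somatrogon, the period tables of this SAP do not count it.

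At stake is the TEAE incidence of the later OLE years and of PEN, which can be understated, and the placing of severe events, which can be credited to the wrong year.

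**Working it through.** The documents state no figure on this point, so there is none to reproduce. The check is a comparison of texts followed by a note on scale.

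**Step 1: what the protocol clause covers.** The worsening limb in protocol 8.5 concerns events present before the first dose. Protocol 6.7.1 names study drug as MOD-4023 or Genotropin, so the first dose is the one given at the start of Period I. The clause covers pre-treatment events that worsen once dosing starts. It does not speak to worsening at the change from Genotropin to somatrogon, at the move to 0.66 mg/kg/week, or at the switch to PEN. The SAP omits the clause and supplies no period-specific rule in its place.

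**Step 2: where an event is counted under SAP 9.1.**

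| Onset | Worsening | Result |
|---|---|---|
| An OLE year | Same year | Counted in that year |
| An OLE year | Later OLE year, or PEN | Counted in the onset year and can appear in the whole-extension summary; not counted in the period of worsening |
| Periods I-II, including on Genotropin | OLE year, or PEN | In no OLE-year or PEN TEAE count; place in the whole-extension summary unclear |
| Any | Entered as a new record with its own start date | Counted in the period of worsening; the documents do not say whether sites do this |

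**Step 3: the severity tables.** Table 14.3.2.3 in SAP 11.1 is a table of TEAEs, so it inherits the start-date rule. Take an event that is mild in OLE Year 1 and severe on PEN. If the maximum grade is used, it appears as severe in Year 1, which SAP 6 reports by assigned dose group. If the initial grade is used, the severe grade does not appear. Neither version shows a severe event on PEN.

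**Step 4: other SAP rules.** Laboratory changes are measured from the first visit of each 12-month period and from the first PEN visit (SAP 9.6). The ECG assessment has a category that includes aggravation (SAP 9.9). Injection-site pain is summarised by its maximum within each period (SAP 9.3). General adverse events have no equivalent.

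**Step 5: scale.** SAP 4.1 gives 53 patients entering the OLE. One patient is 1/53 = 1.9 percentage points of a rate with that denominator. This is the weight of a patient, not an estimate of how many are missed. As an illustration only, assume that between 2% and 10% of patients have an event that only worsens in a given period:

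- expected patients left out: 53 × 0.02 = 1.1 to 53 × 0.10 = 5.3
- chance of at least one: 1 − 0.98^53 = 66% to 1 − 0.90^53 = 99.6%

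The 2% to 10% range is an assumption with no support in the documents. The number entering PEN is not given, so the weight per patient there is unknown.

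**The case against.** The strongest reply is that the protocol clause never covered the OLE transitions. It is tied to the first study dose, and this SAP begins after 12 months of treatment. The departure from protocol 8.5 is therefore narrow, and a period-specific worsening rule goes beyond what the protocol asks. This is correct. It means that copying the clause back would not solve the problem; it does not supply the missing rule.

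A reader might infer that worsened events are never counted. The documents do not support that. An event with onset in the OLE is counted in its onset year, and it can appear in the whole-extension summary, the overall severity table (14.3.1.4) and the listing of all adverse events (16.2.7.1). Events from Periods I-II belong to the Main Study analysis (protocol 8.1), although that analysis does not show what became of them later.

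Some worsening is also visible elsewhere: in the laboratory, ECG and injection-site summaries, in the proportion with IGF-1 SDS above 2 (SAP 9.4), in dose adjustments by reason (SAP 9.13), and in the tables of TEAEs leading to withdrawal, dose reduction or interruption (6.1.1 to 6.1.3). These do not give the incidence of worsened adverse events in general, and the last group consists of TEAE tables.

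Finally, if sites open a new record whenever an event worsens, the start-date rule already works. The documents neither require nor exclude this.

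**Conclusion.** The point holds in this form: SAP 9.1 has no rule for ongoing events that worsen, and does not document this against protocol 8.5. Events with onset in the OLE are counted, but only in the onset year. Events with onset in Periods I-II that worsen in the OLE or on PEN are in none of the OLE-year or PEN TEAE counts. This rests on one assumption, that worsening is not entered as a new record.

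The number of events affected cannot be estimated from the documents. A reader might take 1.9 percentage points, or the 2.6-fold step from 0.25 to 0.66 mg/kg/week (0.66/0.25 = 2.64), as the size of a bias. Neither is. The first is the weight of one patient. The second applies only to patients on the lowest dose; from 0.48 the ratio is 0.66/0.48 = 1.4, Cohort 3 does not change, and PEN continues the current dose. Neither says how often events worsen.

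Nor would a better definition isolate the effect of the dose increase. SAP 6 counts OLE years from the first Period III dose, not from the switch to 0.66 mg/kg/week, and pools dose levels after Year 1. It would serve better for PEN, which has its own start, and for former Genotropin patients, whose first OLE year begins with their first somatrogon dose.

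**What to change.** In SAP 9.1:

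- Define a TEAE of an OLE year or of PEN as an event that starts in the period, or that is ongoing at its start (including from Periods I-II) and increases in severity during it, dated to the increase.
- Apply the same rule to the whole-extension summary, counting each patient once per preferred term and keeping onset and worsening distinguishable.
- State how changes in severity are recorded and which grade the severity tables use.
- Record the difference from protocol 8.5, as SAP 2 requires.

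The cost is a few sentences and minor programming, provided that the records hold dated severity changes. Protocol 5.4.1.1 refers to changes in ongoing events at the first PEN visit, which suggests that some of this information exists, but the documents do not confirm dated grades. Counts will rise slightly, and some events will appear in more than one period, so annual figures should not be added together.

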4.6 REMOVAL, REPLACEMENT, OR EARLY WITHDRAWAL OF PATIENTS FROM THERAPY OR ASSESSMENT

Patients are free to discontinue their participation in the study at any time and without prejudice to further treatment. The Investigator must withdraw any patient from the study if that patient requests to be withdrawn, or if it is determined that continuing in the study would result in a significant safety risk to the patient.

Patients withdrawn from the study after starting treatment with MOD-4023 will not be replaced.

The patient's participation in this study may be discontinued due to the following reasons:

1. Request from regulatory agency, sponsor, primary care physician, or Investigator.
2. Patient (or parent/legal guardian) withdraws consent.
3. Adverse event (AE):
 - Occurrence of a malignancy during the course of study.
 - Evidence of growth of an intracranial tumor during the course of the study.
 - Development of benign intracranial hypertension, if the symptoms return following resumption of drug (after a temporary stop).
 - Occurrence of AE's following which the Investigator or the patient wishes to discontinue treatment (such as, but not limited to, slipped capital femoral epiphysis, scoliosis, avascular necrosis and development of lipoatrophy, etc.).
 - Development of a serious inter-current critical illness.
 - Abnormal laboratory values that affect the patient's safety (if discontinuation is considered necessary by the Investigator or the Sponsor Medical Monitor).

OPKO Biologics	Protocol for Clinical Study CP-4-004	Page 46 of 133
Effective Date: Date of final electronic approval		

4. A severe adverse drug reaction (if discontinuation of study medication is desired by the patient or considered necessary by the investigator or the Sponsor Medical Monitor). If the Investigator decision is made because of a SAE or clinically significant laboratory value, the Medical Monitor is to be alerted immediately.
5. Intake of prohibited concomitant medication.
6. Unsatisfactory treatment response defined as improvement of height SDS of less than 0.2 SDS in a 6-month treatment interval if dose increase at this time point is not feasible (Applicable for periods I-IV)
7. Patient is unwilling or unable to continue the study or is lost-to-follow-up.
8. Patient is non-compliant with study procedures/ study protocol.
9. Investigator decides that withdrawal from the study is in the best interest of the patient:

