5.7.4 Fundoscopy and MRI

Fundoscopy (ophthalmoscopy) will be performed by the Investigator or an ophthalmologist consultant in order to assess signs of increased intracranial pressure prior to initiating or as a result of GH replacement. At screening (or within 6 months prior to screening), to confirm the diagnosis of GH deficiency and to confirm that there is no evidence of pituitary adenoma or any other intracranial tumor, a magnetic resonance imaging scan (MRI) with contrast will be done. It will be performed by the relevant department of the hospital according to the routine practice. During the study, MRIs may be performed per the investigator's discretion, (i.e. when there is suspicion of either growth of pituitary adenoma or any other intracranial tumor).

Fundoscopy will be performed according to the schedule in [Appendix 1: Schedule of Assessments – Main Study to Appendix 5](#).

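### The SAP labels an adverse event of special interest Neoplasias but defines it by a malignancy query alone, so a tumour coded as benign could be left out of that count

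*SAP*

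**What the plan says.** SAP 9.1 states that "AEs will be coded using MedDRA v20.1" and gives a table that maps each AESI to its MedDRA criteria. The row labelled Neoplasias has a single criterion: "Malignancy (SMQ) Full Scope". One other row names a kind of growth, defined as "PT Haemangioma of skin". On use, the SAP says: "Patient incidence of AEs of special interest will also be summarized overall and by SOC through the entire extension period". The planned AESI tables are 4.1, 20, 14.3.2.5 and 14.4.3.5, with Listing 16.2.7.4.

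The protocol covers tumours in several places. Section 4.6 gives malignancy as one reason for which participation may be discontinued, and as a separate item: "Evidence of growth of an intracranial tumor during the course of the study". Section 5.7.4 uses the screening MRI to confirm that "there is no evidence of pituitary adenoma or any other intracranial tumor". During the study it permits further MRI at the investigator's discretion, giving as the example "when there is suspicion of either growth of pituitary adenoma or any other intracranial tumor".

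**The concern.** The label promises tumours in general, while the criterion names malignant ones. A reader of the AESI tables will take the row at its label, so a zero there reads as no tumours. SAP 3.1.1 makes long-term safety the primary objective of the extension analysis, and the protocol treats growth of an intracranial tumour as something to watch for whether or not it is malignant. If the row reaches only malignant terms, the one AESI category that should bring tumour findings together is narrower than the surveillance it summarises. MRI findings do not fill the gap in summary form, because SAP 9.10 provides only a listing.

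**Working it through.** The plan gives no figure for this row, so there is nothing to reproduce. The check is mainly a comparison of texts.

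**1. Does any other AESI row cover benign or intracranial tumours?** Reading the table row by row:
- Neoplasias has one criterion, the malignancy query.
- Haemangioma of skin is one preferred term.
- Intracranial hypertension is "Increased intracranial pressure disorders (high level term [HLT] - All Paths"), which by name covers pressure disorders.
- Intracranial aneurysm covers aneurysms and dissections by name.
- No remaining row names a tumour.

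No other part of the SAP defines or extends Neoplasias.

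**2. Is a single criterion forced by the table's format?** No. The immunogenicity row joins a laboratory result with three queries. The injection site reaction row joins a high level term with selected preferred terms. A composite definition was available.

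**3. Is the protocol's concern wider than malignancy?** Yes. Section 4.6 lists malignancy and intracranial tumour growth as separate items, and does not limit the second to malignant tumours. Section 5.7.4 names pituitary adenoma. Section 1.1.1 lists tumours of the hypothalamic-pituitary region among the causes of acquired growth hormone deficiency.

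**4. What happens to an event coded as benign?** If the malignancy query returns no benign terms, no AESI row collects it, apart from skin haemangioma. It still appears, if reported as a treatment-emergent event, in:
- Tables 14.3.1.2 (overall) and 14.3.2.1 (annual), by system organ class and preferred term;
- Listing 16.2.7.1, all adverse events;
- Table 14.3.1.6 and Listing 16.2.7.3, if it is recorded as leading to withdrawal;
- Listing 16.2.4.4, if an MRI was done.

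**5. Size.** SAP 4.1 gives 53 patients starting the extension. I assume that 53 is the denominator for the whole-extension summary.
- One case: 1/53 = 0.0189, or 1.9%, shown as 0/53 = 0%.
- One-sided 95% upper limit for 0 of 53: 1 − 0.05^(1/53) = 0.055, or 5.5%.
- One-sided exact 95% upper limit for 1 of 53: solve (1 − p)^53 + 53p(1 − p)^52 = 0.05, which gives p = 0.086, or 8.6%.

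For annual and PEN rates SAP 9.1 uses the number of patients at the start of that year or period, so 1.9% applies only to the whole-extension summary.

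**The case against.** The strongest objection is that the contents of the query cannot be seen. The SAP names it and does not reproduce its term list. Full scope appears to be a deliberate choice, since the anaphylaxis, angioedema and hypersensitivity queries in the same table use narrow scope, and it may reach tumours of unspecified nature. This stands. The conclusion is therefore limited to events coded as benign, and even there it relies on the query's name.

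Second, a reader might infer from the separate Haemangioma of skin row that benign growths are known to fall outside Neoplasias. The documents do not support that. The SAP gives no reason for the row and does not say that AESI rows are mutually exclusive, so the sponsor may simply have wanted that term displayed by itself.

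Third, a reader might infer that a child with a growing pituitary tumour would be sent for MRI, leave the study and disappear from the safety results. None of this follows. The MRI is discretionary, section 4.6 says that participation may be discontinued, and the event would remain in the outputs listed in the working.

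Fourth, events should be rare. Exclusion criterion 1 bars past or present intracranial tumour and the screening MRI looks for it, so a case needs a new or missed tumour. This also stands. It lowers the chance that the row is wrong in practice, but those safeguards concern entry and the extension concerns what happens later.

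Finally, the choice of AESI is the sponsor's, and no test or decision rule depends on this row. That is fair, but the label should still match what is counted.

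**Conclusion.** The mismatch between label and definition is real. The Neoplasias row is defined by a malignancy query, no other AESI row covers benign or intracranial tumours in general, and the protocol treats intracranial tumour growth as a matter separate from malignancy. On the assumption that the query returns no term coded as benign, one benign tumour in the whole extension would turn a true 1.9% into a reported 0%. The one-sided upper limit attached to the row would be 5.5% instead of 8.6%. The fault is one of classification in the AESI tables. It does not hide the event and is unlikely to arise often. It is worth correcting before the tables are run, because the row serves the primary safety objective and, with events this rare, the definition can decide what is reported.

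**What to change.** In the AESI table of SAP 9.1, define Neoplasias as the malignancy query plus benign and unspecified neoplasm terms, including pituitary and other intracranial tumours. In Tables 4.1, 20, 14.3.2.5 and 14.4.3.5, show malignant tumours separately from benign or intracranial ones. State whether a skin haemangioma is counted in both rows or only in its own.

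At minimum, rename the row Malignancies and add a separate row for benign and intracranial tumours. Renaming alone would make the label true but would still leave no AESI row for the intracranial tumours that the protocol watches for.

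The cost is small: a change to the definition table and a few extra table rows. Adverse events are already to be coded in MedDRA, so no new data are needed and clinical management is unaffected. The drawback is that trivial benign lesions will also appear, which separate display keeps in proportion.
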